8.9. Limitations of the research methods

Hawthorne effect can only be evaluated for the SOC comparison. This does not give definite evidence about whether the prognostic or predictive effect of RELVAR would differ in the general population. This information could only truly be obtained following use of RELVAR in the general population.

There is no direct metric by which 'representativeness' of the Salford cohort can be measured. Early explorations of this will be made in a companion project – see Annex 2.1.

WWEpi Project number: PRJ2282

While both the SLS and CPRD use GP data, some data (hospital validated COPD diagnoses, pneumonia data, pharmacy data) for participants in SLS are collected using a different mechanism to CPRD. In this study protocol, only serious pneumonia defined by hospitalization will be assessed, which is a subset of total pneumonia cases recorded in the SLS. Hence any differences (either in representativeness or treatment response) observed between the SLS and non-SLS cohorts could be attributed to differences in data quality and the data collection mechanism. This will be mitigated by an additional comparison of SLS data with CPRD data from within Greater Manchester.

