8.4. Data sources

The three main data sources are SLS, CPRD and SIR.

The Salford Lung Study (SLS) is described in [14]. In brief, it is a pragmatic trial, carried out in Salford, UK, to evaluate the relative effectiveness and safety of RELVAR compared with SOC. There are two separate studies within the SLS; one for COPD and the other for asthma. For this protocol, the SLS data refers to SLS for COPD only.

WWEpi Project number: PRJ2282

The CPRD is a primary care database consisting of a subset of GP practices across the UK. This will be linked to Hospital Episode Statistics (HES), socio-economic status (SES) and Office of National Statistics (ONS) datasets. For brevity, the linked dataset will henceforth be referred to as CPRD.

The SIR is a comprehensive primary and secondary care database detailing healthcare contacts, diagnostic tests and prescriptions of all patients registered with a GP in Salford, UK.

There are a range of subsets and derivations of the data sources that will be considered for this study, listed here for clarity.

CPRD: CPRD – all practices, all COPD patients

CPRD-GM: CPRD – practices/patients in Greater Manchester only, all COPD patients

CPRD-xGM: CPRD – excluding practices/patients in Greater Manchester, all COPD patients

CPRD-GM-IC: CPRD – practices/patients in Greater Manchester only, COPD patients meeting SLS inclusion criteria only

CPRD-xGM-IC: CPRD – excluding practices/patients in Greater Manchester, COPD patients meeting SLS inclusion criteria only

SLS-E: SLS – all eligible. Not all of these are enrolled (some decline)

SLS: SLS - all enrolled

SLS-SOC: SLS – SOC arm only

SIR: SIR – all COPD patients

SIR-IC: SIR - COPD patients meeting SLS inclusion criteria only

In the CPRD, data linkage will be subject to a lag due to the delayed availability of HES and ONS data. Fully linked data will only be available up to a certain date when analyses are undertaken, and as such, primary analyses will be restricted to include SLS enrolled patients up to that date. Subsequent analyses will be conducted once linkage is available for the entire recruitment period. As capture of events of serious pneumonia (as defined in the context of this study) is dependent on records of hospitalisation, PO3 will be analysed when fully linked CPRD-HES data are available.

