8.7. Data analysis

8.7.1. Essential analysis

All analyses will be conducted using SAS.

For PO1, distributions of the confounders and effect modifiers (as listed in Section 8.3.3) will be tabulated – summarised as proportions in each category for binary and categorical variables, and means/medians and standard deviations for continuous variables. Graphical visualisations will also be produced to aid interpretation (for example, boxplots to characterise age distributions in each population, stacked bar charts to visualise SES by population). This will be done for a series of the derived populations to separate out true differences in demographics in Salford and differences that arise as a consequence of data quality issues etc. The following comparisons will be of interest:

- CPRD-GM v CPRD-xGM: to give an indication of true demographic difference from the same data source.
- CPRD-GM-IC v CPRD-xGM-IC: as above, but restricted to patients meeting the inclusion criteria.
- SIR v CPRD-GM: to give an indication of differences arising as a consequence of selection bias of CPRD practices, and through data quality issues etc.
- SIR-IC v CPRD-GM-IC: as above, but restricted to patients meeting the inclusion criteria.
- SIR-IC v SLS-E: to give an indication of recruitment bias and physician researcher bias (at the approach stage).
- SIR-IC v SLS: to give an indication of recruitment bias (at recruitment stage).
- SLS v CPRD-xGM-IC: to indicate the difference between trial recruited, and those
 meeting the inclusion criteria outside of Salford. This is the key comparison for
 addressing PO1.

WWEpi Project number: PRJ2282

We will then move on to explicit modelling of regional variation of the characteristics within CPRD for the emboldened comparison (SLS v CPRD-xGM-IC) to ascertain whether the characteristics observed within Salford are unusual by comparison with CPRD-xGM-IC. We will take local authority regional level (anonymised) as the comparable unit to the study region for SLS. SLS will be considered unusual on a given demographic if an appropriately chosen summary statistic for that demographic (mean for continuous variables) falls outside the 2.5-97.5 percentile range.

For PO2, we will commence with exploratory analyses, similar to described above, to explore the distributions of the primary and secondary endpoints.

Hawthorne effect will be evaluated in two different ways.

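### Comparing SLS with Greater Manchester CPRD addresses region, not the data-collection difference that section 8.9 says it mitigates, so capture and Hawthorne effects remain inseparable in PO3

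*Protocol*

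**What the plan says.** Section 8.9 states that several kinds of data, pneumonia among them, "for participants in SLS are collected using a different mechanism to CPRD". It notes that PO3 is limited to hospitalised pneumonia, and still concludes that differences between SLS and non-SLS cohorts "could be attributed to differences in data quality and the data collection mechanism". The remedy follows at once: "This will be mitigated by an additional comparison of SLS data with CPRD data from within Greater Manchester".

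Section 8.4 defines CPRD-GM as "CPRD – practices/patients in Greater Manchester only, all COPD patients". It is the same database as the main comparator, CPRD-xGM, with a different area filter.

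Section 8.7.1 lists seven contrasts for PO1, and SLS v CPRD-GM is not among them. The contrast given the task of showing data-quality differences is SIR v CPRD-GM, with a version restricted to patients meeting the SLS criteria (SIR-IC v CPRD-GM-IC). Its purpose is "to give an indication of differences arising as a consequence of selection bias of CPRD practices, and through data quality issues etc". It is listed where patient characteristics are tabulated.

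For PO2, section 8.7.1 pools SLS and CPRD in a multilevel model with SLS as its own region. An SLS region effect outside the 2.5-97.5 percentile range is read as evidence of a Hawthorne effect. PO3 follows the same approach.

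**The concern.** The limitation concerns how events are recorded in SLS compared with CPRD. The remedy changes where the CPRD patients live. Since CPRD-GM records events as the rest of CPRD does, the extra comparison carries the same SLS-against-CPRD capture difference as the main one.

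Two things are at stake. First, PO3 is a co-primary objective that sections 5 and 11.2 schedule for regulatory reporting, and the protocol presents a known source of artefact as mitigated when the named comparison does not reach it. Second, if SLS v CPRD-xGM-IC and SLS v CPRD-GM-IC agree, section 8.9 invites the reader to take this as reassurance about data capture. Agreement would show only that Greater Manchester resembles the rest of CPRD on that outcome.

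**Working it through.** The protocol gives no figure to reproduce. The check is which components each contrast can separate.

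**Inputs**
- SLS and CPRD capture pneumonia differently; the difference is not quantified (8.9).
- CPRD-GM and CPRD-xGM are one source split by area (8.4).
- PO3 uses the PO2 model, with SLS as a separate region (8.7.1).
- Values of capture and region below are assumptions for illustration. Capture ratios from 0.7 to 1.4 were tried.

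**Step 1: decompose each rate ratio.** Let H be the trial or Hawthorne effect, R the Greater Manchester v elsewhere effect, and C the SLS:CPRD capture ratio.
- SLS / CPRD-xGM = H × R × C
- SLS / CPRD-GM = H × C
- CPRD-GM / CPRD-xGM = R

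The first divided by the second is (H × R × C) / (H × C) = R. On the log scale the three contrasts have rank 2 for three unknowns. R and the product H × C can be estimated; H and C separately cannot. CPRD practice selection and case mix are left out here and would only add unknowns.

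**Step 2: put numbers in.**

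| H | R | C | SLS/xGM | SLS/GM | GM/xGM |
|---|---|---|---|---|---|
| 1.00 | 1.2 | 0.80 | 0.96 | 0.80 | 1.20 |
| 0.80 | 1.2 | 1.00 | 0.96 | 0.80 | 1.20 |
| 1.00 | 1.0 | 1.25 | 1.25 | 1.25 | 1.00 |
| 1.25 | 1.0 | 1.00 | 1.25 | 1.25 | 1.00 |

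Rows 1 and 2 give identical observed ratios, one from capture alone and the other from a trial effect alone. Rows 3 and 4 do the same. In rows 3 and 4 the two SLS contrasts agree exactly, although in row 3 the whole departure from 1 is artefact. With H = 1, SLS/GM equals C at every value tried from 0.7 to 1.4.

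**Step 3: the PO3 model.** Every SLS patient has SLS capture and every CPRD patient has CPRD capture. Data source therefore coincides with the SLS region, and the SLS region effect absorbs C with H.

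**Step 4: is it only a code-list problem?** No. The Table 1 codes not marked No and the list in section 3 of the code-list annex are identical: 25 bacterial + 18 fungal + 5 abscess + 26 mycobacterial + 11 viral + 9 unspecified + 2 other = 96 in each, with no differences. What remains is the collection mechanism.

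**Step 5: what SIR-IC v CPRD-GM-IC on outcome rates would add.** If SIR captured pneumonia as SLS does, and nothing else differed, this contrast would equal C and the rank would rise from 2 to 3. In general it is C′ × S × H′, where C′ is SIR:CPRD capture, S is CPRD practice selection, and H′ is any change in Salford practice that reaches patients outside the trial. Take H = H′ = 0.90 and C = C′ = S = 1 as an illustration. Then SLS/GM = 0.90 and SIR-IC/CPRD-GM-IC = 0.90, and dividing one by the other gives 0.90 / 0.90 = 1.00, which erases the effect being sought.

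**The case against.** The best defence is that the protocol discloses the artefact openly and has narrowed it. PO3 counts hospitalised events only, waits for fully linked CPRD-HES data (8.4), and uses one ICD-10 list on both sides. Those points stand and reduce definitional differences. But section 8.9 itself says, after noting the hospital restriction, that the collection mechanism could still explain a difference.

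A second defence is that coding quality may vary by area, so that a local comparator shares some of it with SLS. The documents say nothing either way. If true, that part behaves like region and is removed; the SLS-against-CPRD mechanism part that 8.9 describes is not.

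A third is that endpoint comparisons in Salford are not ruled out. Section 8.7.1 opens PO2 with exploratory endpoint analyses, section 8.3.2 says Salford patients outside SLS will be examined, and SO3 compares outcomes before and after SLS began. This also stands in part. None of these names a pneumonia contrast for capture, and SO3 is stated to support PO2. The CPRD-Salford exacerbation analysis in the code-list annex uses primary care data only, so it cannot inform hospitalised pneumonia. The unseen SAP may add analyses, but it cannot make SLS v CPRD-GM remove this difference.

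A reader might also infer that the SIR-IC v CPRD-GM-IC ratio could correct the PO3 and PO2 estimates. The documents do not support that. Section 6.2 places the Hawthorne effect in the behaviour of GPs and nurses, who may also treat Salford patients outside the trial. Section 8.7.1 says the contrast also reflects CPRD practice selection. Nothing says that SIR records hospitalised pneumonia as SLS does.

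**Conclusion.** The point holds in a limited form. The mitigation claimed in section 8.9 does not address the limitation it is attached to: SLS v CPRD-GM removes region and none of the SLS-against-CPRD mechanism difference. Capture and Hawthorne effects remain inseparable in PO3, both in that contrast and in the multilevel model. This rests on CPRD-GM and CPRD-xGM sharing one capture mechanism, which follows from section 8.4, and on effects multiplying.

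A reader might infer that PO3 is biased by a known amount, say 10% to 25%, or in a known direction. The document gives no capture sensitivities and no pneumonia rates, so neither can be computed; the ratios above are illustrations. Nor does the document say how agreement between the two SLS contrasts will be interpreted, so misreading is a risk to close off rather than a planned step. PO3 compares standard of care with standard of care, so the point says nothing about RELVAR itself.

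**What to change.** 1. Replace the mitigation sentence in section 8.9. Say that SLS v CPRD-GM addresses geography and not the data mechanism, and that agreement between SLS v CPRD-xGM-IC and SLS v CPRD-GM-IC is not evidence against a data artefact. This costs nothing.

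2. Extend the planned SIR-IC v CPRD-GM-IC contrast from characteristics to serious pneumonia and exacerbation rates. Remove all SLS participants from SIR-IC, since section 8.2.2 excludes only the RELVAR arm. Where data allow, run it in the period before SLS started, so that changes in Salford practice do not contaminate it.

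3. Report it as a labelled sensitivity analysis that qualifies the reading of PO3 and PO2, not as a factor applied to the estimates. State its limits: it includes CPRD practice selection, assumes SIR and SLS capture hospitalised pneumonia alike, and may be imprecise (the protocol gives no size for CPRD-GM).

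The cost is a modest extra analysis on sources the protocol already names. No change to the pneumonia code list is needed.

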8.9.1. Study closure/uninterpretability of results

Not applicable.

PROTECTION OF HUMAN SUBJECTS

9.1. Ethical approval and subject consent

Individual subject consent is not required as this work is using research data. Internal ethical approval will be sought from the University of Manchester.

Linkage of the CPRD to other datasets such as HES is undertaken by a trusted third party (the Health and Social Care Information Centre). The identifiers (date of birth, gender, NHS number, postcode of residence) required for linkage are sent directly from the originating general practice to the trusted third party. CPRD holds only a local patient identifier which is meaningful only at the patients' registered general practice. This identifier is pseudonymised a second time before being made available to researchers and analysts with access to the database.

CPRD's processes have been reviewed by the Confidentiality Advisory Group (CAG) and approved by the Health Research Authority (HRA) and Secretary of State to process patient identifiable information without consent under Regulation 5 of the Health Service (Control of Patient Information) Regulations 2002. This effectively removes the obligation to obtain patient consent for the use of confidential patient information for conducting purely observational research using CPRD databases, and associated linked datasets. This approval is conditional on approval of a study protocol by the CPRD Independent Scientific Advisory Committee (ISAC). In addition to ISAC approval, the protocol will be reviewed by GSK Worldwide Epidemiology Protocol Review Forum.

9.2. Subject confidentiality

The SLS data will be anonymised at source by the SLS team, before this is passed to University of Manchester.

The CPRD only contains fully de-identified patient data. No patient identifiable information will be available to the study team, or to GSK. All data held and processed by CPRD and any other study partners will be done so in compliance with the relevant legal obligations including the Data Protection Act 1998.

WWEpi Project number: PRJ2282

All data will be held on a secure computer network, with access restricted to authorised users.

10. MANAGEMENT AND REPORTING OF ADVERSE EVENTS/ADVERSE REACTIONS

This is a retrospective study. From the CPRD, free text data will not be available to allow causality determination of any potential adverse events. Adverse events arising from the SLS trial will have previously been reported appropriately during the trial period.

11. PLANS FOR DISSEMINATING AND COMMUNICATING STUDY RESULTS

11.1. Target Audience

This work is targeted 1) internally at GSK, 2) regulators and 3) the wider scientific community; in order to understand the SLS in wider context. Results will be disseminated externally primarily by manuscripts.

11.2. Study reporting and publications

Reporting and publications according to the following table:

Deliverable	Timelines
Agreed Protocol for GSK protocol-review forum	November, 2014
Completion of Statistical analyses plan. Development of programs for analyses.	November 2014 – 1st October 2015
Analyses of PO2 (COPD exacerbation data) using final SLS data: First report with PO1/PO2 to GSK	By 29 th April 2016
Share output from Primary Objectives with SLS Scientific Committee; and CHESS Steering Committee	9-10 th May 2016
First manuscript developed and ready for submission with SLS paper to Thorax based PO1 and PO2 data	June-July 2016
Analysis for P03 and draft tables circulated	November 2016
Draft complete study report with PO1/PO2/PO3 to GSK	December 2016
Regulatory reporting of PO3	Q1 2017

WWEpi Project number: PRJ2282

Final follow-up manuscript	Q1-2 2017	
----------------------------	-----------	--

In addition, we will present the results of the study at international respiratory conferences as appropriate. The study protocol and results will be posted to GSK Clinical Study Register as per GSK SOPs.

ANNEX 1. LIST OF STAND-ALONE DOCUMENTS

Annex 1a: System Level Security Policy (SLSP) for Study

System Details

1. The System shall be known as

CHESS: CPRD-COPD Hawthorne Effect Study in Salford: A UK cohort study to characterise patients enrolled in the Salford Lung Study and to evaluate a potential Hawthorne effect

- 2. The System's responsible owner shall be PPD
- 3. The System's Caldicott Guardian or Data Controller shall be

System Security

 Security of the system shall be governed by the corporate security policy of University of Manchester

http://documents.manchester.ac.uk/display.aspx?DocID=6525 (policy)

http://documents.manchester.ac.uk/display.aspx?DocID=8039 (responsibilities)

5. The System's responsible security manager shall be:

University IT Security Coordinator

6. The security manager duties shall include:

Devise, implement, enforce and review the University's IT security and data handling policies.

Being the first point of contact for any security related queries or concerns. Being consulted on and providing the final sign-off for any requests for change to any aspects of IT security for the system.

- 7. The System shall incorporate the following security countermeasures:
 - Physical Security Data Processing: The researchers are based within Vaughan House which is swipe card access only from reception into the building. Staff and Postgraduate students must have their University swipe cards enabled for access to the building. The offices are also locked when vacant.
 - Physical Security Data Hosting: The data will be stored within Personal Drives (P: Drives) hosted on the University's network storage infrastructure which is the recommended location for storing sensitive or critical University

WWEpi Project number: PRJ2282

data. The storage infrastructure is hosted across two data centres (approx. 2KM apart) for resilience and disaster recovery purposes. Physical access to the data centres is strictly limited to data centre staff and a limited number of authorised IT Services staff. The data centres are protected by physical and electronic access security systems, swipe card access in and out of the data centres and CCTV coverage. The data centres are locked down out of hours and access is discouraged, but can be arranged by prior agreement with the data centre manager.

- Access Control and Privilege Management: The data will be hosted on authorised system user's P: drives which are strictly controlled data shares within the University's network storage infrastructure to which only the owner of the P: Drive has access permissions. The data share will only be accessed via a mapped network drive from PCs identified for research data processing.
- Network Security Measures: Network access control lists prevent PCs outside of the campus LAN from accessing the network storage infrastructure.
- Other Data Processing: Four PCs have been identified for processing the research data. Once the PC has loaded the operating system a local, password protected computer account is required to login to the PC. This account is unique to the primary user of the computer and only the account owner knows the password. The PC has the Windows firewall enabled and configured to prevent remote access. The PCs have been configured to automatically update their antivirus signatures daily and have been configured to download and install any Microsoft operating system and application security patches automatically from the Microsoft update service.

System Management

8. The System shall be developed / provided by:

University of Manchester, Faculty of Medical & Human Sciences, Information Services
University of Manchester, IT Services Division

9. The System shall be implemented & maintained by:

University of Manchester, Faculty of Medical & Human Sciences, Information Services will configure and maintain the security aspects of the PC, user accounts and access controls for the data share on the network storage infrastructure.

University of Manchester, IT Services Division (ITSD) will be responsible for providing secure, reliable data hosting on the network storage infrastructure.

Servers procured by ITSD include maintenance on either 3 or 5 year agreements depending on the Service requirements. Supplier engineers replace any defectives items and may request access to the Data Centre. In addition Data centre staff are trained and able to carry out component replacements on behalf of the suppliers.

WWEpi Project number: PRJ2282

Storage arrays are procured with support and maintenance included as part of a 3 year package. The SAN Arrays in the central ITS Data Centres are supplied by EMC and have allocated engineers who are familiar with our site configuration and conversant in maintaining the equipment and advising on future changes.

To ensure the security of University hosted infrastructure systems, all system changes must be authorised via the change management process. Any proposed system changes are recorded as requests for change (RFC's) and authorised by the change advisory board (CAB).

10. The System shall be shared or used by the following organisations:

GSK will have direct access to the system for quality checking purposes.

System Design

11. The System shall comprise:

The research PCs connect to the University's network via access switches which are located in data cabinets within secure, dedicated comms rooms. The switches are logically segregated into separate VLAN's for network efficiency and security. The access switches then connect to the University's core router and onto perimeter routers via multiple paths for resilient access to the data centres where the network storage infrastructure is hosted. The perimeter routers connect onto the JANET network and the wider internet. The perimeter routers are configured with access control lists which provide security for incoming network traffic. A network diagram can be found at the end of this SLSP.

The operating system on the PCs identified for data processing require local username and password authentication for access. The P: drives on the network require username and password authentication also.

Operational Processes

12. The patient identifiable / sensitive data will be collected:

Datasets will be pseudonymised at source by providers. No patient identifiable or sensitive information will be processed.

13. The data will be stored:

The data will be stored electronically in R and SAS file formats. The data will be made available to authorised members of research staff via P: drives hosted on the University's network storage infrastructure housed in the University's data centres.

14. The data will be processed:

WWEpi Project number: PRJ2282

Four University approved desktop PCs will be used to process the data. The PCs will not cache copies of the data and all data will be stored on the network storage infrastructure.

The University's Information Handling Policy sets out how digital information should be handled. This includes confidentiality, integrity and availability and the use of encryption tools for the protection of sensitive information and communications.

http://www.itservices.manchester.ac.uk/medialibrary/pdf/secureguidance/GP-InformationHandling.pdf

15. The System's authorised users shall be:

University	of	Manche	ster:
PPD			

- 1 x Research Associate, to be appointed.

GSK

TBA by GSK.

The system's authorised users are all University members of staff and individuals designated by GSK. The data will not be accessible by any other third party organisations

16. When the system or its data has completed its purpose / has become redundant or is no longer needed, the following methods will be adopted to dispose of equipment, back-up media or other stored data:

Sensitive material on removable media are deleted as soon as possible. Printed materials and CD/DVDs containing sensitive information are shredded when no longer required. When the analysis is completed the researcher will delete files. All items of equipment containing storage media shall be checked to ensure that any sensitive data and licensed software has been removed or securely overwritten.

Desktop PCs are disposed of when replaced via a recognised disposal company, Computer Disposals LTD (CDL). CDL erase the hard drives to Government Restricted Standard SEAP (UK), which is three overwrites plus an additional verification pass. A certificate is produced for every successfully data erased hard drive to include the make, model and serial number of the hard drive. Any hard drive that fails the data erase process is degaussed on site at CDL using the latest CESG approved degausses and forwarded for recycling.

University IT Services has a policy of securely wiping network storage infrastructure arrays onsite prior to disposal. Disks are securely erased by software aligned to the DoD5220-22M standard and are then disposed of via CDL who also wipe the disks as per their procedure outlined above.

WWEpi Project number: PRJ2282

System Audit

17. The System shall benefit from the following internal / external audit arrangements:

In 2006, the University's IT Services undertook (in conjunction with KPMG) a comprehensive IT Risk Management Benchmarking exercise to appraise the University's approach to the management of IT-related risks. The review was intended to provide a benchmark upon which to build the maturity of IT Services activities over a number of years. Whilst the exercise found a number of positive areas within IT, it also identified a number of areas for development and agreed management action plans to address the issues raised.

A follow-up review was conducted during 2009 by UNIAC, the University's internal auditing body. This review: (i) revisited each original recommendation, ascertaining progress to date (supported by testing where appropriate) and its ongoing relevance; (ii) commented on the adequacy of the actions to date; (iii) proposed revised action plans for previous actions remaining outstanding; (iv) made additional suggestions over and above the agreed action.

The original KPMG report contained over thirty high and medium level recommendations and, realistically, a number of them would take a considerable period to fully implement. The follow-up review in 2009 concluded that: (i) recommendations had been fully implemented with no further action required in seven areas; (ii) good progress had been made towards implementing a further fifteen recommendations; (iii) some progress had been made towards implementing a further six recommendations; (iv) limited progress had been made towards implementing a final four recommendations.

Overall, the report concluded that progress has been encouraging and indicated that IT Services management had provided adequate focus to improving the management of IT risks.

Future auditing arrangements include regular audits agreed with internal and external auditors. The Director of IT Services meets the UNIAC Director annually to agree the internal programme; the external programme is agreed via the University's Audit Committee.

18. The System shall be risk assessed every 12 months

The University's Compliance and Risk Officer (CRO) is responsible for ensuring that the University is meeting its many statutory and regulatory compliance obligations. The CRO is responsible for supporting the University's risk management process, all aspects of risk management and has developed a risk management framework.

All major University functional areas (including IT Services) are required to conduct annual risk assessments and to review risk registers on a quarterly basis. Risk registers are submitted to the University's CRO for reporting to the

WWEpi Project number: PRJ2282

University's Risk Management Committee. Risk management is a specific responsibility of heads of operational areas.

System Protection

19. The System shall benefit from the following resilience / contingency / disaster recovery arrangements:

The University's storage infrastructure is hosted and replicated across two data centres (approx. 2KM apart) for resilience and disaster recovery purposes.

The University's IT Services Division (ITSD) utilises Legato Networker Backup domains. Supporting infrastructure comprises disk libraries and both physical and virtual tape libraries. Cross data centre backup is performed, so services hosted within data centre 1 (Kilburn) are backed up to data centre 2 (Reynold) and vice versa

Backup/recovery plans are documented as part of the service install process during the commissioning of a specific service. Each Service is responsible for its business continuity and disaster recovery plans, to which ITSD feed in its technical recovery plans

ITSD operates a change management process. All proposed changes to infrastructure hosted, maintained and administered by ITSD are recorded via the RFC process with changes being authorised by a Change Advisory Board (CAB).

20. In the event of serious disruption or total system failure, business continuity shall be provided by the following means:

The University's geographically dispersed, replicated, twin data centre approach with cross site backup has been designed to be as fault tolerant as possible and to provide business continuity in the event of a data centre failure. Should a situation arise where both data centres became unavailable then the University's disaster recovery plans relating to the failed system would be implemented.

21. In the event of a security or confidentiality breach occurring the following procedure shall be followed:

Information on the procedure for reporting a security or confidentiality breach is available from the following link on the University's Secure-IT website: http://www.itservices.manchester.ac.uk/secure-it/reporting/

SSP Ownership

22. This SLSP shall be the responsibility of:

22.1 - Shall be reviewed on an annual basis for its completeness and for relevant update.

WWEpi Project number: PRJ2282

23. The SLSP shall be available / distributed to:

Authorised GSK and University of Manchester staff involved in research activities or members of IT staff assisting with the completion of SLSP forms.

- Through which secure means:

[figure not shown]
The SLSP document will be distributed to authorised GSK and University of Manchester staff via the internal email system.

Data Protection Registration

24. Please confirm that your organisation has Data Protection Registration to cover the purposes of analysis and for the classes of data requested.

http://www.ico.gov.uk/ESDWebPages/search.asp - . Registration No: Z6787610

Network diagram as referenced in the System Design section of the SLSP

WWEpi Project number: PRJ2282

